15.1. Information to patients

During the pre-inclusion visit (at the onset of the inclusion criteria) the critical care physician will verbally inform the patient about the aims of the study, and the patient will also be given an explanation sheet. The patient's consent to take part in the study will be collected and recorded in the patient's medical record. The explanation will be repeated by the investigator (physiotherapist) at the time of the LUS. All of the examinations are part of the usual management of such patients. The research will be managed by the Paris St Joseph Hospital Network for French centres and Ethics committee of St Vincent's Hospital for the Australian centres. The information on the research will be provided to the patient (*cf. annexe 5a*) or, if this is impossible because of the emergency situation, to a member of the patient's family (*cf. annexe 5b*). If a patient could not be informed and could not sign the consent form for this research, and/or if a patient was included with the consent of a family member, the patient will be informed and will be invited to continue to participate in the research as soon as he/she has recovered his/her cognitive abilities.

F_{IO_2} = fraction of inspired oxygen

*All values were significant ($p > 0.003$)

Annexe 2a: Clinical hypothesis model by physiotherapist

Clinical examination is compatible with retained airway secretions			
	Auscultation	Palpation	Cough/Suction
	Rhonchi, crackles, wheeze	Palpable chest wall fremitus	Producing sputum
Clinical examination is compatible with bronchospasm			
Chest X-rays	Auscultation		Inspection
"Hyperinflated lungs"	Expiratory Wheeze		Prolonged expiratory phase Accessory inspiratory muscles use
Clinical examination is compatible with pneumonia pattern			
Chest X-rays	Auscultation	Palpation/percussion	Inspection
Lobar consolidation or interstitial opacities +/- airbronchogram No volume loss	Fine crackles Decreased or abolished vesicular sound Bronchial breath sound	Dullness Increased vocal fremitus	+/- focal decreased chest mobility
Clinical examination is compatible with atelectasis pattern (passive or obstructive active mechanism)			
Chest X-rays	Auscultation	Palpation/percussion	Inspection
Lobar consolidation +/- airbronchogram Volume loss	Abolished vesicular sound	Dullness Increased vocal fremitus	+/- focal abolished chest mobility
Clinical examination is compatible with pleural effusion (PE) / (+/- passive atelectasis)			
Chest X-rays	Auscultation	Palpation/percussion	Inspection
Blunting of the costophrenic and/or cardiophrenic angles Meniscus Mediastinal shift (large PE)	Abolished vesicular sound	Dullness Decreased vocal fremitus Pleural rub sound	+/- focal abolished chest mobility on the side of the PE
Clinical examination is compatible with acute pulmonary oedema (cardiogenic or not)			
Chest X-rays	Auscultation	Palpation/percussion	Inspection
Cephalization of pulmonary vessels Kerley B lines Peri-bronchial cuffing « Bat wing » pattern	Bilateral and diffuse fine crackles +/- Wheeze	Palpable chest wall fremitus	Inspiratory dyspnea
Clinical examination is compatible with pneumothorax			
Chest X-rays	Auscultation	Palpation/percussion	Inspection
Air without lung markings in the least dependant part of the chest unless loculated	Abolished vesicular sound	Hyper tympanic Abolished vocal fremitus	Decreased chest mobility
Clinical examination is compatible with reduced of aeration at the most dependent parts of the lungs			
Chest X-rays	Auscultation	Palpation/percussion	Inspection
Lobar consolidation or interstitial opacities at the inferior parts of the lungs	Decreased or abolished vesicular sound at the lung bases	Dullness at the lung bases	Decreased chest mobility
Clinical examination is compatible with diaphragm dysfunction			
Chest X-rays	Auscultation		Inspection
Elevation of hemidiaphragm cupola	Decreased or abolished of basal vesicular sound		Decreased chest mobility Thoracic inspiration Paradoxical respiration
The bilateral or unilateral nature of diaphragm dysfunction is defined by the unilateral or bilateral nature of the previous signs.			
Clinical examination is inconclusive			
No syndrome clearly defined			

[figure not shown]
Annexe 2b: Chest physiotherapy treatment modalities

Clinical hypothesis	Chest physiotherapy treatment		
Retained airway secretions	Airway clearance techniques (Rib cage compressions, manual assisted cough, manual lung hyperinflation, ventilator hyperinflation, MIE, ETS/NTS, patient positioning)		
Bronchospasm	Bronchodilators inhalation		
Pneumonia pattern	Unilateral	Bilateral	
	Non intubated	Laterocubitus (diseased lung uppermost) + NIV/CPAP	Seated position + NIV/CPAP
	Intubated	Laterocubitus (diseased lung uppermost) + PEEP	Seated position, prone position + PEEP
Obstructive Atelectasis pattern	Lobar	Entire lung	
	Non intubated	Laterocubitus (diseased lung uppermost) + NIV	
	Intubated	Laterocubitus (diseased lung uppermost) + hyperinflation/PEEP	Refer to medical staff
Pleural effusion/Passive atelectasis	Unilateral	First, refer to medical staff	
	Non intubated	Laterocubitus (diseased lung uppermost) + NIV/CPAP	Seated position + NIV/CPAP
	Intubated	Laterocubitus(diseased lung uppermost)+ PEEP	Seated position + PEEP
Acute pulmonary oedema	Refer to medical staff		
	Non intubated	Seated position + NIV	
	Intubated	Seated position	
Pneumothorax	Refer to medical staff		
Reduced aeration at dependent parts of the lungs	Seated or upright position, mobilization out of bed		
Diaphragm dysfunction	Seated position, recovery monitoring, IMT		
Clinical examination is inconclusive	Refer to medical staff		

MIE = Mechanical Insufflation-Exsufflation ; ETS/NTS = Endotracheal/Nasotracheal suction ; NIV = Noninvasive ventilation ; CPAP = Continuous positive airway pressure ; PEEP = Positive end expiratory pressure ; IMT = Inspiratory muscle training

Annexe 3a: Lung and diaphragm ultrasound procedures (16)

Lung assessment

PSL: Parasternal line; AAL: Anterior axillary line; PAL: Posterior axillary line

Scanning procedure

[figure not shown]
Interstitial syndrome: Investigation is performed at the anterior and lateral thoracic areas. A positive region is defined by the presence of three or more B-lines in a longitudinal plane between two ribs, and a positive exam suggests the presence of two or more positive regions. A convex probe is used.

Consolidation: Examination begins with the lung area of interest (refer to clinical assessment) and may involve the entire lung if necessary. A convex probe is used.

Pneumothorax: In the supine patient, the sonographic technique consists of exploration of the least gravitationally dependent areas progressing laterally. A convex or a linear probe may be used.

Pleural effusion: In the supine patient, the ultrasound probe is placed in the postero-inferior area in the transverse view. The maximum distance between the parietal and visceral pleura (PLD) is measured 3 cm above the inferior pole of the lung at the end of expiration.

Diaphragm assessment – excursion and thickness *(If ventilated patient use PSV mode with PS = 7 and PEEP = 0)*

Diaphragm excursion: Anterior subcostal approach: the probe is placed between the anterior axillary line and the mid-clavicular line. B-mode is initially used to determine the best approach and select the exploration line. After the diaphragm is identified, excursion measurements are performed in M-mode: the diaphragm moves toward the probe during inspiration and away from it during expiration. The distance between the end-inspiration and end-expiration points defines the diaphragm excursion. A diaphragm excursion < 2.5 cm (Lerolle Chest, 2009) indicates a diaphragm dysfunction.

Diaphragm thickening: the probe is placed in an intercostal space between the mid-axillary line and the anterior axillary line, 0.5 cm to 2 cm below the costo-diaphragmatic sinus. In B-mode, the diaphragm is observed as a structure made of three distinct layers: a non-echogenic central layer bordered by two echogenic layers. The diaphragm thickening fraction (DTF) measurement is obtained in B-mode using the following formula: $DTF (\%) = [(end-inspiration\ thickness - end-expiration\ thickness) / (end-expiration\ thickness) \times 100]$. A DTF < 25% indicates a diaphragm dysfunction.

Annexe 3b: LUS Semiology

	
NORMAL PATTERN
 
A. Seashore sign (left, M-mode): Tissues above the pleural line are motionless and generate horizontal lines (sea). Below the pleural line, structures (i.e., lung and visceral pleura) are in motion and generate a sandy pattern. Bat sign (right, B-mode): In the intercostal space, the shape of the superior and inferior ribs and pleural line (i.e., hyperechoic line) appear in the shape of a bat. A-lines (right, B-mode): Horizontal repetition artifacts of the pleural line (big arrows) that indicate the presence of lung aeration.
	
	
INTERSTITIAL SYNDROME
 
B.B-lines: Comet-tail artifacts (arrows) that arise from the pleural lines and erase A-lines are nearly always long and always move with lung sliding.
	
	
C. PLEURAL EFFUSION
 
Pleural effusion appears as dependent and anechoic (ie, free of echoes) structures. Pleural effusion occurs between the diaphragm and the pleura, and conducts ultrasounds, C. Sinusoid sign (left, M-mode): During inspiration, the visceral pleura moves toward the parietal pleura; this sign indicates a free pleural effusion. Quad sign (right, B-mode): The visceral pleural, parietal pleura and shadows of the ribs form a quad; this sign indicates a pleural effusion in an intercostal space.
 
Quantification of pleural effusion: patient in supine with mild trunk elevation at 15°. Ultrasound probe is moved in cranial direction in posterior axillary line. The transverse section perpendicular to the body axis is obtained with pleural separation visible as an anechoic or hypoechoic layer between two pleural layers. The maximal distance between parietal and visceral pleura (Sep) is measured off line at the lung base after freezing the image in end-expiration.
	
	
CONSOLIDATION
 
D. Shred sign (B-mode): A deep boundary (arrow) with a shredded appearance indicates a partial lobar consolidation. Note the presence of an air bronchogram (Br).
	
	
CONSOLIDATION
 
E. Tissue-like sign (B-mode) A tissue-like pattern arising from the pleural line (or visceral pleura) of a complete lobar consolidation.
	
PNEUMOTHORAX
 
Lung point (M-mode): Refers to the absence of any sliding or moving B-lines at the physical locations where the transition into an area of sliding occurs. Stratospheric sign (M mode): absence of pleural sliding (P).

P = pleural line; Rs = superiorrib; Ri = inferiorrib; Pp = parietal pleura; Pv = visceral pleura; Pe = pleural effusion; C =lung consolidation; D = diaphragm; Br = air bronchogram.

Annexe 4: Lung and diaphragm ultrasound scan report

VENTILATOR SETTINGS (Surround the mode and fill the settings at the moment of LUS examination)						
Mode	ACV	SIMV	PCV	PSV	NIV	Spontaneously Breathing
Settings	Tidal volume =		PEEP =	PS =	PEEP =	

PNEUMOTHORAX				
Right	Present	Absent	Left	Absent
If present, locate the lung point in the diagram below (place an « X »)				

LUNG AERATION					
	LAT	ANT	ANT	LAT	
POST					POST
Superior	Pleural sliding Lung pulse	Pleural sliding Lung pulse	Pleural sliding Lung pulse	Pleural sliding Lung pulse	Pleural sliding Lung pulse
Inferior	Pleural sliding Lung pulse	Pleural sliding Lung pulse	Pleural sliding Lung pulse	Pleural sliding Lung pulse	Pleural sliding Lung pulse
Indicate level of lung aeration (0, 1, 2, 3) in the above diagram			LUS score = /36		
When lung consolidation is present, indicate the appropriate letter(s) (in the above diagram, following the « 3 ») :					
a. Deep limit with Shred sign		d. Static air bronchogram		g. Fluid bronchogram	
b. Deep limit well defined		e. Punctiform air bronchogram		h. Vascular pattern	
c. Dynamic air bronchogram		f. Linear air bronchogram			

PLEURAL EFFUSION								
	Right				Left			
PLD (cm)								
Pattern	Anechoic	Heterogeneously echogenic	Homogeneously echogenic	Septated	Anechoic	Heterogeneously echogenic	Homogeneously echogenic	Septated

DIAPHRAGM				
	Right		Left	
tdi/tde (cm)				
DTF (%)				
EXC (cm)				

ULTRASOUND DIAGNOSTIC				Scan quality:
Normal		Pneumothorax (L), (R) or Both		
Alveolar-interstitial syndrome		Focal	Diffuse	Good
		Homogeneous	Heterogeneous	
Lung consolidation		Moderate	Severe	Poor
		Atelectasis pattern		
Pneumonia pattern		Atelectasis pattern		Sonographer:
Unilateral (L) or (R)	Bilateral	Obstructive	Passive	
Pleural effusion		Unilateral (L) or (R)	Bilateral	
		Transudative pattern	Exsudative pattern	
Diaphragm dysfunction		Loss of aeration in the most dependent parts of the lungs		
Unilateral (L) or (R)	Bilateral	No conclusion

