5.1. Inclusion criteria

Patients presenting the following criteria will be eligible:

- Hypoxemia ($SpO_2/FiO_2 < 315$ (15)) (indication for chest physiotherapy) (*cf. annexe 1*);
- Medical prescription for chest physiotherapy;
- First session of chest physiotherapy;
- Chest X-ray < 12h available;
- Physiotherapist/operator qualified in LUS available;
- Patient's consent.

5.2.Exclusion criteria

Patients presenting the following criteria will not be eligible:

[figure not shown]
- Presence of a contra-indication for chest physiotherapy;
- Absence of hypoxemia;
- Absence of a prescription for chest physiotherapy;
- Absence of a chest X-ray < 12h from the time of physiotherapy assessment;
- Physiotherapist/operator qualified in LUS not available;
- Lung and diaphragm US not possible (surgical emphysema, dressing, scarring, drains etc.);
- Refusal of the patient or a relative to participate in the study;
- Patients to be discharged on the day of the study;
- Patients in palliative care;
- Withdrawal/limitations of medical care with impending death.

6. Methodology:

6.1.Type of study

This is a multi-centre prospective (patients enrolled on admission) interventional study evaluating a routine assessment/treatment. The study intends to assess the impact of lung and diaphragm ultrasound on the usual physiotherapist's clinical decision-making process. Each included patient will be clinically assessed by a clinical physiotherapist, and then will have a lung and diaphragm ultrasound by another physiotherapist/operator blinded to the clinical assessment findings. The lung and diaphragm ultrasound findings will then be presented to both the intensivist and clinical physiotherapist to evaluate the impact on the independent clinical decision-making by both the intensivist and physiotherapist.

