6.5.2. Procedure 2: Lung and diaphragm US

6.5.2.1. *Ultrasound physiotherapist/operator*

The LUS will be performed by the physiotherapist/operator, who will be blinded to the clinical evaluation by clinical physiotherapist, the patient's status including the Chest X-rays and CT-scan findings and all of other clinical information. The operator will not take part in the management of the patients concerned.

The ultrasound training of the operator in the French ICU was performed as follows:

- Two days academic theoretical and practical training;
- One year supervised lung ultrasound practice: more than 200 supervised thoracic ultrasound examinations performed;
- Two years autonomous thoracic ultrasound practice.

The Australian ICU used a modified version of this training program with a one day theoretical and practical training course and supervised lung ultrasound practice.

6.5.2.2. *Ultrasound examination modalities*

A referent intensivist will be present when LUS is performed by a french physiotherapist, in order to control the adequate realization of LUS examination. Referent intensivists are trained to LUS. [name] [name] (Forcilles' Hospital), [name] [name] (St. Joseph's Hospital) and Pr [name] (University Hospital of Dijon) will be referent intensivists.

The CX 50 (Philips) or Edge (Sonosite) ultrasound machine, with 3.5 MHz convex and 10 MHz linear probes, will be used. The convex probe will be used to assess the lung (interstitial syndrome, consolidation, pneumothorax, diaphragm excursion and pleural effusion) and the linear probe will be used to assess to evaluate diaphragm thickness.

The patient will be in semirecumbent position (head 30° from bed) for LUS imaging. Two lines delimit the axillary space: the anterior and posterior axillary lines. These lines define

areas of investigation for each hemithorax—anterior, lateral, and posterior—each of which is divided into upper and lower parts. Each hemithorax includes 6 examination areas (*cf annexe 3a*). The locations of the liver and spleen allow for the identification of the right and left diaphragm cupolas, which separate the thoracic and abdominal compartment. The probe will be used to explore each intercostal space using a longitudinal view. Specific examination modalities for the diaphragm ultrasound are defined in annexe 3a.

6.5.2.3. *Lung and diaphragm ultrasound semiology*

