The basics lung ultrasound semiology is described in annexe 3b. The following syndromes will be searched for: normal profile, alveolar-interstitial syndrome, pulmonary consolidation, pleural effusion, pneumothorax and diaphragm dysfunction (16).

The ultrasound syndromes are defined by the following signs in a scanned for the in six-lung zones of each chest wall of the patient:

Normal lung:

- Bat sign;
- A lines;
- Pleural sliding (seashore sign).

A normal profile is compatible with presence of tracheo-bronchial retained secretions and bronchospasm.

Alveolar-interstitial syndrome(16–18):

- A positive region is defined by the presence of three or more B-lines in a longitudinal plane between two ribs;
- In the anterior and lateral thoracic areas;
- Multiple and well-defined B-lines: moderate loss of lung aeration;
- Confluent B-lines: severe loss of lung aeration.

The presence of a focal sonographic pattern of interstitial syndrome is compatible with pneumonia, atelectasis or pulmonary contusion.

The presence of multiple diffuse bilateral B-lines is compatible with pulmonary oedema or ARDS. In the case of pulmonary oedema, the interstitial syndrome is diffuse, homogeneous and bilateral. In the case of ARDS, the interstitial syndrome is diffuse, heterogeneous, bilateral and associated with pleural abnormalities and sub-pleural consolidations.

Lung consolidation:

- Subpleural echo-poor region or tissue-like echo-structure;
- Atelectasis pattern(19,20):

- Abolished pleural sliding;
 - Static air bronchogram;
 - Lung pulse;
 - Passive atelectasis due to compression from the surrounding pleural effusion: homogeneous echogenic structure into the pleural effusion, with smooth margin and linear air bronchogram(21).
- Pneumonia pattern(22–25):
- Irregular deep margin when the consolidation is partial;
 - Regular deep margin when consolidation involves an entire lobe;
 - Static or dynamic air bronchogram;
 - Fluid bronchogram;
 - Vascular pattern;
 - Bilateral or unilateral.

The aim of physiotherapist is not to identify the medical diagnosis. Regarding the presence of the interstitial syndrome and lung consolidation, the aim is to also define the level of lung aeration present in each of the 12 lung zones:

- Normal aeration (N): presence of lung sliding with A-lines or fewer than two isolated B-lines;
- Moderate loss of lung aeration (B1): multiple, well-defined B-lines (B1 lines);

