7.4.4. Ultrasound physiotherapist/operator visit

Following the clinical physiotherapist visit, the ultrasound physiotherapist/operator performs a lung and diaphragm ultrasound. He is blinded to the patient's status and clinical physiotherapist examination. He/she is not involved in patient management or patient clinical decision-making. The ultrasound findings are recorded in the LUS report (*cfannexe4*). The LUS report is reported to the clinical physiotherapist and to the intensivist. The ultrasound diagnosis(es) is recorded.

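### The consolidation line of Annexe 3a starts the scan from the clinical assessment, which the blinded ultrasound operator is not allowed to know

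*Combined protocol and SAP*

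**What the plan says.** Section 6.1 has each patient assessed by a clinical physiotherapist, after which the patient "will have a lung and diaphragm ultrasound by another physiotherapist/operator blinded to the clinical assessment findings". Section 6.5.1.4 repeats this. Section 6.5.2.1 is the fullest statement: "The LUS will be performed by the physiotherapist/operator, who will be blinded to the clinical evaluation by clinical physiotherapist", and the blinding extends to "the patient's status including the Chest X-rays and CT-scan findings and all of other clinical information". Section 7.4.4 says of the operator: "He is blinded to the patient's status and clinical physiotherapist examination".

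On the extent of the scan, section 6.5.2.2 sets six areas per hemithorax and has the probe cover every intercostal space. Section 6.5.2.3 states the aim to "define the level of lung aeration present in each of the 12 lung zones", with consolidation scoring 3 in a total that runs from 0 to 36. The report form in Annexe 4 asks for those zone scores and that total.

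Annexe 3a, the ultrasound procedures annexe, says under consolidation: "Examination begins with the lung area of interest (refer to clinical assessment) and may involve the entire lung if necessary". Its lines on interstitial syndrome, pneumothorax, pleural effusion and the diaphragm do not refer to the clinical assessment.

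**The concern.** The operator cannot both be kept from the clinical findings and begin where those findings point. Being told which area is of interest reveals the suspected side and site.

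The ultrasound reading is one half of every agreement judgement in the analysis. Section 8.2.1 defines an event as ultrasound compatible with the clinical diagnosis, and a non-event as the reverse. Section 8.2.3 cross-tabulates clinical against ultrasound diagnosis for kappa, and agreement is secondary criterion 2 in section 4.2. Consolidation scanning feeds two of the eight kappa categories: T1 (pneumonia/consolidation) and T2 (atelectasis). The signs that separate these patterns, such as the margin and the type of air bronchogram, call for judgement and are open to expectation. If the clinical hypothesis guides the reading, agreement is no longer agreement between independent assessments.

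**Working it through.** The plan gives no figure to reproduce here, so the main check is of the text.

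**Blinding.** Sections 6.1, 6.5.1.4, 6.5.2.1 and 7.4.4 withhold the clinical findings from the operator, and 6.5.2.1 withholds all other clinical information too. The consolidation line in Annexe 3a directs the operator to the clinical assessment. This cannot mean an assessment by the operator, because none is described. No section reconciles the two instructions.

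**Extent.** Sections 6.5.2.2 and 6.5.2.3 and Annexe 4 call for a whole-chest examination with every zone scored. The Annexe 3a line leaves the whole-lung scan for consolidation to discretion. This is a second, smaller conflict.

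**Primary index.** Write u_E and u_N for the proportions of events and non-events in which treatment was modified. In section 8.2.1 the up and down proportions sum to 1 within each group, so

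NRI = (2u_E − 1) − (2u_N − 1) = 2(u_E − u_N).

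Suppose steering moves some patients from non-event to event, and a proportion r of them have modified treatment. Then u_E moves towards r and u_N moves away from r.

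- r above both proportions: u_E rises, u_N falls, NRI rises.
- r below both: u_E falls, u_N rises, NRI falls.
- r between them: both move the same way, and the sign depends on group sizes.

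The documents give none of these proportions, so the direction of the change in NRI is not determined.

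**Agreement, as illustration only.** Formula from section 8.2.3: κ = (Pa − Pe)/(1 − Pe). All inputs are assumed except the planned 150 patients (section 8.1). For consolidation present or absent, take 40 positive on both, 25 clinical only, 20 scan only, 65 neither.

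- Pa = (40 + 65)/150 = 0.70.
- Pe = (65 × 60 + 85 × 90)/150² = 0.513.
- κ = (0.70 − 0.513)/(1 − 0.513) = 0.38.

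Now let 10%, 20% or 30% of the 25 clinical-only patients become positive on both. The agreeing counts are 107.5, 110 and 112.5, so Pa = 0.717, 0.733 and 0.750. Pe = 0.511, 0.509 and 0.507. Then κ = 0.42, 0.46 and 0.49. If the same shares of the 20 scan-only patients also moved to neither, κ would be 0.45, 0.51 and 0.57, but that requires lesions outside the suspected site to be missed.

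This is a two-category kappa, whereas the plan has eight categories. A rough version on that scale, with Pe assumed and fixed at 0.20 and 10% to 30% of all discordant readings made concordant:

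| Assumed Pa | κ before | κ after 10% | κ after 30% |
|---|---|---|---|
| 0.40 | 0.25 | 0.33 | 0.48 |
| 0.50 | 0.38 | 0.44 | 0.56 |
| 0.60 | 0.50 | 0.55 | 0.65 |

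For example, at Pa = 0.50 a 10% shift gives Pa = 0.50 + 0.10 × 0.50 = 0.55 and κ = (0.55 − 0.20)/0.80 = 0.44. The table treats every discordant reading as exposed, although only consolidation readings are.

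**The case against.** The strongest reply is that the body of the protocol governs. It states the blinding four times, against one parenthetical in an annexe. Section 6.5.2.2 refers to Annexe 3a for the examination areas and the diaphragm technique, not for an order of scanning for consolidation. Sections 7.4.4 and 7.4.5 send the ultrasound report to the clinical physiotherapist and the intensivist, and describe no transfer of clinical findings to the operator. This stands as far as conduct goes: a reader might infer that blinding was broken, and the documents do not support that. It does not remove the conflict, because the line sits in the annexe that sets out the scanning procedure.

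A reader might also infer that operators would stop at the suspected area and miss disease elsewhere. The annexe wording permits a wider scan and does not forbid it, and a score out of 36 cannot be completed without all 12 zones. In the French centres a referent intensivist also checks that the scan is adequate (section 6.5.2.2) and validates the report (section 6.5.2.4). This largely answers the missed-lesion worry. It does not answer the loss of independence: an operator who scans all 12 zones but starts from the clinical assessment still knows what is suspected.

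Finally, the kappa figures rest on assumed inputs, and a claim that the primary index is biased in a given direction would need data that the documents lack. Both objections stand.

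**Conclusion.** The point holds as an internal contradiction with a material consequence if the annexe line is followed. The operator would then know the suspected site before reading the consolidation patterns. Clinical-ultrasound agreement would tend to be inflated, and patients would shift between the two NRI denominators. The tendency to inflate assumes that expectation pulls readings towards the clinical hypothesis. The size of the effect, and the direction of any change in the NRI, cannot be determined from the documents. The kappa values above show scale only and should not be cited as estimates.

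The contradiction is limited to the consolidation line. Left as it is, centres could resolve it differently, which would blur the NRI by centre planned in section 8.2.2. It should be corrected. Confidence is high for the textual conflict and much lower for the amount of bias.

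**What to change.** In the consolidation line of Annexe 3a, delete the parenthetical that refers to the clinical assessment and the closing words that make the whole-lung scan conditional. State instead that all 12 zones are examined in every patient, in an order that does not depend on the clinical findings. Add that the ultrasound diagnosis is recorded before the operator has any contact with those findings, which makes explicit the sequence already set out in sections 7.4.4 and 7.4.5.

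The cost is a short wording change. All 12 zones are already to be scored, so no scanning is added, and no treatment rule or analysis changes. If patients were scanned before the correction, ask each centre which instruction its operators followed and report the answer with the agreement results.
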